11.1.1. Chest X-ray or CT

A chest X-ray (or CT scan), for purposes of determining participant eligibility, will be performed only at Screening Visit 1b. The maximum combined number of chest X-rays and/or CT scans must not exceed 2 for screening.

11.1.2. Smoking Status Review

At the Screening Visits 1a and 1b, information on smoking history (including cigarettes, electronic cigarettes, pipes, marijuana, vaporizers, and cigars), smoking duration (in years), and smoking quantities (in pack-years) will be collected. Former smokers are defined as individuals who have stopped smoking for at least 6 months prior to Screening Visit 1b. The number of pack-years will be calculated using the formula:

Number of pack years = (number of cigarettes per day / 20) × number of years smoked
(eg, 20 cigarettes per day for 10 years, or 10 cigarettes per day for 20 years both equal 10 pack-years).

One pack of cigarettes a day for 1 year is equivalent to:

- 1 cigar or pipe per day for 1 year.
- Smoked hookah or shisha =1 session per day for 1 year.
- Vaped e-cigarettes =0.5 mL e-liquid per day for 1 year, or =1 cartridge/tank/pod per day for 1 year.
- 1 use of marijuana per day for 1 year.

Recent smoking status will be reviewed at timepoints specified in the SoA (Table 5).

11.1.3. Concomitant Medications

Concomitant medication assessments should include prior or current information regarding all prescription, illicit, nonprescription, or alternative medications (including herbal products, vitamins, and contraceptive medications). Use of any palliative or supportive care medications (eg, analgesics, anti-emetics, antidiarrheals, hematopoietic growth factors, transfusions) should be noted.

See Section 8.2 for more information.

11.1.4. Demographic/Medical and Surgical History and Other Baseline Characteristics

Demographic information collected will include age and sex, along with ethnicity and race as described by the participant. Other baseline characteristics include height, weight, and body mass index. Medical history includes COPD history, acute exacerbation history, past and current medical conditions (such as cardiovascular and cerebrovascular medical history and surgical history), and substance usage.

11.2. Safety Parameters

Safety will be evaluated by assessment of reported AEs, including SAEs and AESIs, DILI, UADEs, safety laboratory evaluations (hematology, clinical chemistry, and urinalysis), vital signs, physical examinations including injection site evaluation, oxygen saturation detected via pulse oximetry, ECG, and concomitant medication/treatment review. The planned timepoints are provided in the SoA (Table 5).

At baseline (Visit 2 Day 0), participants will be monitored for a minimum of 2 hours after IP administration.

11.2.1. Vital Signs and Oxygen Saturation

Vital signs, including body temperature, respiratory rate (breaths per minute), pulse (beats per minute), and blood pressure (BP; mmHg), will be measured in the seated position following at least 5 minutes rest at the timepoints specified in the SoA (Table 5).

BP and pulse measurements will be assessed with a completely automated device whenever possible. Manual techniques will be used only if an automated device is not available. Vital signs will be measured prior to the spirometry maneuvers.

Oxygen saturation will be measured by pulse oximeter as indicated in the SoA.

Participants will be monitored for a minimum of 2 hours after IP administration. Vital sign measurements will be performed pre-injection, at 30 minutes (± 10 minutes) post-injection and then at 1 hour (± 10 minutes) and 2 hours (± 15 minutes) post-injection as indicated in the SoA. Any abnormal findings that are new or worsened in severity and clinically significant, in the opinion of the Investigator, will be recorded as an AE. Vital sign measurements will be recorded in the eCRF.

11.2.2. Height and Weight

Height and weight will be measured at time points per the SoA (Table 5). Height will only be measured at Screening Visit 1a or 1b. The participant's height must be measured without shoes and weight must be determined in indoor clothing and without shoes.

11.2.3. Physical Examination

Complete and symptom-directed physical examinations will be performed at timepoints per the SoA (Table 5).

A complete physical examination will cover general appearance, dermatology, head, ears, eyes, nose, throat, respiratory, cardiovascular, abdominal, neurological, musculoskeletal, and lymphatic body systems.

Symptom-directed physical examinations can be performed at the Investigator's discretion at timepoints allowed per the SoA.

Findings from physical examinations will be documented in the appropriate sections of the eCRF. Abnormal findings identified during physical examination will be evaluated and documented by the Investigator as to whether the abnormality is an AE or medical history.

11.2.4. Electrocardiograms

Twelve-lead ECGs will be taken at timepoints per the SoA (Table 5).

ECGs will be taken using an approved ECG machine. It is recommended that the same ECG machine is used for each assessment. The ECG measurements are collected and assessed at local sites.

All ECG measurements will be performed with the participant resting in a supine position for approximately 5 minutes before each reading and should be carried out after measurement of vital signs and before spirometry. ECGs should be performed before blood is drawn during visits requiring blood draws.

The following parameters will be recorded:

- Ventricular rate.
- PR interval.
- QRS duration.
- RR interval.
- QT interval.
- QT interval corrected for heart rate using Fridericia's formula (QTcF).

Note: The QTcF will be centrally calculated for standardization of reporting across all centers.

The Investigator/Investigator's designee will be responsible for reviewing the ECG to assess whether it is within reference limits and to determine the clinical significance of all abnormal ECG results ('clinically significant' or 'not clinically significant'). A copy of the ECG

assessment must be kept in the participant's file at the site. The ECG strips or reports will be retained with the source.

11.2.5. Injection Site Reaction Assessment

Assessment of the planned injection sites will be performed prior to dosing and again following the injections prior to release of the participant from the clinic (if applicable), and the additional scheduled timepoints per the SoA (Table 5).

An assessment tool is provided in Appendix D as an aid in the assessment of common symptoms of injection site reaction. The use of the assessment tool is encouraged but the Investigator may use their own judgement and description of symptoms in the assessment of injection sites following administration of IP.

Participants will be monitored for a minimum of 2 hours after IP administration. Injection sites will be assessed at 30 minutes (± 10 minutes) post-injection and then at 2 hours (± 30 minutes) post-injection as indicated in the SoA (Table 5).

Prior to the participant being discharged from the clinic visit, the injection sites should be observed, and the participant queried for the following:

- Pain.
- Erythema/redness.
- Itching/scratching/pruritus.
- Warm to touch.

Additionally, when the participant returns for their next visit, the site staff should inquire about any signs/symptoms of an injection site reaction that occurred after discharge from the prior clinic visit.

An injection site reaction should be reported as an AE if the Investigator judges the reaction as clinically significant. If the AE of Injection Site Reaction lasts longer than 24 hours and the severity is Common Terminology Criteria for Adverse Events (CTCAE) Grade ≥ 3 , it will be considered an AESI as defined in Section 11.3.3 and should be reported as described in Section 11.7.2.

See Appendix D for an injection site reaction assessment tool.

11.2.6. Laboratory Assessments

Safety laboratory samples (hematology, clinical chemistry, urinalysis) will be performed at visits according to the SoA (Table 5). See Appendix C for the list of clinical laboratory tests to be performed.

Standard laboratory hematology, clinical chemistry, and urinalysis will be analyzed by a qualified central laboratory. Any safety laboratory tests completed as part of the assessment and treatment of the COPD exacerbation may be used for Screening (eg, clinical chemistry, hematology, urinalysis).

Due to the short screening window, local laboratory results will be used for the purpose of determining the participant's eligibility for randomization. Local laboratory samples should be

taken at Screening Visit 1b and the results should be received and reviewed prior to randomization to allow review of the applicable eligibility criteria. If local laboratory results from the assessment of the current COPD exacerbation are already available within 48 hours prior to Screening Visit 1b, these results can be used for determination of participant's eligibility. For all randomized participants, a sample for central laboratory analysis should be obtained before IP administration on Day 0 as baseline.

The Investigator must review the laboratory report, document this review, and record any clinically relevant changes occurring during the trial in the AE section of the eCRF. The laboratory reports must be filed with the source documents. Clinically significant abnormal laboratory findings are those which are not associated with the underlying disease, unless judged by the Investigator to be more severe than expected for the participant's condition.

All laboratory tests with values considered clinically significantly abnormal during participation in the trial or within 28 days after the dose of IP should be repeated until the values return to normal or baseline or are no longer considered clinically significant by the Investigator or medical monitor.

If such values do not return to normal/baseline within a period of time judged reasonable by the Investigator, the etiology should be identified and the Sponsor notified.

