8.4.3. Blinding and Unblinding

This is a double-blind trial; neither the participants nor the Investigator will be aware of the treatment assignment for the participants. Blinding will be maintained throughout the trial by the use of active and placebo treatment of similar appearance and volume-matched dosing.

All Sponsor staff or designee will remain blinded to the treatment allocation until after the trial database is locked with the following exceptions:

- The independent statistician preparing the randomization codes, providing data to the DMC, and conducting the unblinded IA.
- A limited number of the Sponsor's senior management team (independent of the clinical trial team) who will receive results from the IA.
- The staff of the Sponsor or designee responsible for packaging IP.

- The staff of the Sponsor or pharmacovigilance vendor responsible for assessment and reporting of a suspected unexpected serious adverse reaction (SUSAR).
- The staff of contract research organizations (CROs) involved in processing the PK samples.
- The quality assurance auditors, where necessary.

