10.1. Treatment Failure

Treatment failure is defined as death due to any cause, (re)admission to a hospital for COPD, ED (re)visit or unscheduled medical visit for worsening of COPD symptoms, or the necessity to intensify pharmacologic treatment (including second course of systemic steroids for COPD exacerbation) within 28 days after randomization.

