12.2. Pharmacodynamics

Biomarkers of type 2 inflammation will be assessed over the course of participants' treatment including blood eosinophil count, eotaxin-3, C-reactive protein (CRP), total immunoglobulin E (IgE), and TARC as specified in the SoA (Table 5). Additionally, pulmonary and activation-regulated chemokine (PARC) and fibrinogen will be assessed.

Blood will be collected for measurement of these biomarkers of inflammation associated with COPD as specified in the SoA.

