12.2.1. Fractional Exhaled Nitric Oxide

FeNO will be measured using a NIOX VERO[®] Airway Inflammation Monitor, or equivalent device according to the SoA (Table 5). The FeNO test will be performed prior to spirometry. Participants should not eat or drink for 1 hour prior to having the FeNO test.

If Visit 1b and Visit 2 are the same day, then FeNO does not need to be repeated.

Further details on the procedure for measuring FeNO with NIOX will be provided in a separate instruction manual

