APPENDIX C. CLINICAL SAFETY LABORATORY ASSESSMENTS

Laboratory Tests	Parameters	
Hematology	
 • Platelet count 	
	
 • Red blood cell (RBC) count 	
	
 • White blood cell (WBC) count with differential: neutrophils, lymphocytes, monocytes, eosinophils, basophils 	
	
 • Hemoglobin 	
	
 • Hematocrit 	
Clinical Chemistry	
 • Blood urea nitrogen (BUN) • Potassium • Creatinine • Sodium • Calcium • Glucose • Chloride • Bicarbonate • Uric acid • Albumin • C-reactive protein^a • Creatine Phosphokinase (CPK) • Triglycerides 	
 • Aspartate aminotransferase (AST) • Alanine aminotransferase (ALT) • Alkaline phosphatase (ALP) • Gamma-glutamyltransferase (GGT) • Lactate dehydrogenase (LDH) • Total and direct bilirubin • Total protein • Total cholesterol
Routine Urinalysis	
 • Specific gravity • pH, glucose, protein, blood, ketones, bilirubin, urobilinogen, nitrite, leukocyte esterase • Microscopic examination (if blood or protein is abnormal) 	
Pregnancy Testing	
 • Highly sensitive human chorionic gonadotropin pregnancy test (as needed for women of childbearing potential) (serum at screening only, urine at subsequent visits) 	

^a C-reactive protein is a pharmacodynamic marker.

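### Investigators must review post-dose reports carrying eosinophils and CRP, both named pharmacodynamic markers, while one component of the primary endpoint is discretionary; no masking is stated

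*Protocol*

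**What the plan says.** All references are to the protocol.

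- **Review duty (11.2.6).** Standard hematology and chemistry go to a central laboratory. The text then says "The Investigator must review the laboratory report, document this review", requires clinically relevant changes to be recorded, and has the reports filed with source documents. No result is excepted.
- **Panel content (Appendix C).** Hematology includes "White blood cell (WBC) count with differential: neutrophils, lymphocytes, monocytes, eosinophils, basophils". CRP is listed under clinical chemistry, with the footnote "C-reactive protein is a pharmacodynamic marker".
- **Role of the markers (Table 2, 12.2).** The pharmacodynamic list reads "blood eosinophil count, eotaxin-3, C-reactive protein (CRP), total immunoglobulin E (IgE), and TARC". FeNO is a pharmacodynamic endpoint too.
- **Timing (Table 5).** After dosing, the panel is drawn at Day 7 ±2, Day 28 ±3 and Day 56 ±3.
- **Blinding (8.4.3).** "Blinding will be maintained throughout the trial by the use of active and placebo treatment of similar appearance and volume-matched dosing." The listed exceptions for Sponsor staff or designees include contract staff processing pharmacokinetic samples. Nothing is said about pharmacodynamic results returned to sites.
- **Primary endpoint (10.1).** Failure includes death, COPD admission, emergency or unscheduled visits, "or the necessity to intensify pharmacologic treatment (including second course of systemic steroids for COPD exacerbation) within 28 days after randomization".
- **Adjudication (6.8).** The only adjudication committee covers cardiovascular events and cardiovascular deaths.

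**The concern.** A double-blind design with a partly judgement-based endpoint relies on the people making the judgement having no post-dose information related to treatment. Here the plan requires the Investigator to read two markers that it classes as pharmacodynamic, at a time when most of the 28-day window is still to run.

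Bias could enter in two ways. A clinician might form a view of the allocation from the value. Or a clinician might react to the value itself: section 4.1 describes eosinophil counts as a guide to personalized COPD treatment, so a Week 1 count could prompt a change in therapy, and that change can count as a failure. In the second case no guess about the arm is needed. A laboratory effect of the drug would pass into the primary endpoint without a clinical difference behind it.

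Moderate exacerbations in section 10.2 are also defined by treatment given, so the exacerbation secondary endpoints share the exposure.

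**Working it through.** **Setting the passages side by side**

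1. Are eosinophils and CRP on a report the Investigator must read? Yes (11.2.6 with Appendix C).
2. Does a post-dose draw fall inside the primary window? Yes, at Day 7 ±2 (Table 5). The Day 28 ±3 draw falls at the end of the window and adds little. No panel is scheduled on Days 1, 2, 3 or 14.
3. Is any post-dose result masked? None is stated (8.4.3, 11.2.6).
4. Is part of the endpoint discretionary? Yes. Intensification in 10.1 has no objective trigger. Section 8.2.2.1 leaves treatment of subsequent exacerbations to the Investigator or other qualified personnel and allows changes to maintenance regimens.
5. Is that component adjudicated? No (6.8).

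**Reproducing the plan's own figure.** Section 13.2 assumes 22.5% against 45%, 152 evaluable (76 per arm), two-sided 5%, and claims at least 80% power.

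- Mean rate = (0.45 + 0.225)/2 = 0.3375.
- SE0 = √(2 × 0.3375 × 0.6625 / 76) = 0.0767.
- SE1 = √((0.45 × 0.55 + 0.225 × 0.775) / 76) = 0.0745.
- Power = Φ((0.225 − 1.96 × 0.0767)/0.0745) = Φ(1.00) = 84.2%. Exact enumeration gives 84.4%; a continuity-corrected formula gives about 79%.
- 152/0.95 = 160.

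The stated power is reproduced without continuity correction and is not in dispute.

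**Illustration of sensitivity.** The size of any bias is an assumption; the protocol supplies none. Take no true effect, a failure rate p in both arms, and a spurious reduction s in recorded failures on active. The two-sided rejection probability is

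Φ((s − 1.96·SE0)/SE1) + Φ((−s − 1.96·SE0)/SE1).

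For p = 45% and s = 5 points:

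- SE0 = √(2 × 0.425 × 0.575/76) = 0.0802.
- SE1 = √((0.2475 + 0.24)/76) = 0.0801.
- The two terms are Φ(−1.34) = 0.090 and Φ(−2.59) = 0.005, which sum to 9.5%.

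| Assumed shift s | Participants of 76 | Normal approximation, p = 30%, 35%, 45% | Exact enumeration, same p |
|---|---|---|---|
| 2 points | 1.5 | 5.84%, 5.77%, 5.70% | 5.77%, 5.81%, 5.74% |
| 3 points | 2.3 | 6.93%, 6.76%, 6.60% | 6.86%, 6.77%, 6.71% |
| 5 points | 3.8 | 10.57%, 10.05%, 9.53% | 10.52%, 9.99%, 9.85% |

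With s = 0 the exact rate is 4.92%, 5.11% and 4.90%. These figures use an unstratified pooled z-test as a stand-in for the Cochran-Mantel-Haenszel test in 13.4.5. They show how few discretionary calls would matter if they leaned one way. They are no evidence that any do.

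**The case against.** The case on the other side is substantial, and most of it stands as a limit on the point.

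- **No arm-revealing signal is shown.** A reader might infer that these values tell the Investigator the treatment. The protocol does not support that. The rademikibart biomarker effect it reports is on TARC (4.2.2), which is not in the Appendix C panel. It gives no direction or size for blood eosinophils or CRP, and 13.4.10 calls the biomarker analyses exploratory.
- **Corticosteroids blur the reading.** All participants need systemic corticosteroids, defined as 5 days in 8.2.2.1. Inclusion criterion 11 advises sampling eosinophils beforehand, which implies an effect on the count. A 5-day course begun by Day 0 ends before the Day 7 draw, but only shortly before its early window, and the duration may be modified. This weakens inference about the arm; it does not stop a clinician reacting to the number.
- **The exposed part of the endpoint is limited.** One might infer that the same Investigator decides every component. Section 10.1 names no decision-maker, and Table 3 foresees prescribing by physicians outside the trial. Patients may start urgent visits themselves, and death is objective. Failures before the Day 7 results arrive cannot be affected.
- **FeNO.** It is tempting to say that Investigators see post-dose FeNO. Section 12.2.1 says "The FeNO test will be performed prior to spirometry" on a monitor and refers to a separate manual, but does not say who sees the reading. The FeNO rows of Table 5 are not in the text available here. FeNO is therefore secondary to this point.
- **Masking has a price.** Parasitic and opportunistic infections are events of special interest (11.3.3), and Investigators must judge and repeat abnormal laboratory values.

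What remains is that the plan requires disclosure of two named pharmacodynamic markers to people who may judge a discretionary, unadjudicated component. A laboratory manual might restrict this, but the review duty in 11.2.6 points the other way.

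**Conclusion.** The point holds as an open route to bias that is cheap to close. The protocol's own text puts eosinophils and CRP before the Investigator at Day 7, states no masking, and leaves treatment intensification to judgement without adjudication.

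It does not establish that unblinding occurs or that the Type I error is actually raised. The range of about 6% to 10% depends wholly on an assumed net shift of 2 to 5 points in one direction; reactions to a marker that did not differ between arms would produce no such shift. The practical exposure is the part of the window after the Day 7 results and, mainly, the intensification component. That supports a modest change to blinding procedures, not a claim that the primary result would be unreliable.

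**What to change.** 1. State in 8.4.3 and 11.2.6 that post-dose eosinophil counts and CRP are withheld from central laboratory reports to sites and to the blinded sponsor team until database lock. Withhold other differential values only as far as needed to prevent back-calculation of eosinophils.
2. Amend the review duty in 11.2.6 so that it covers the results actually released.
3. Send values crossing a prespecified safety alert limit through the existing unblinded safety or Data Monitoring Committee channels, and describe that path.
4. Where post-dose FeNO is measured at site, keep the reading from staff who decide on treatment or record failure, when existing staffing allows.

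Eligibility uses local pre-dose results, so post-dose masking does not affect it.

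**Cost.** Report configuration, protocol wording and an alert path. The Investigator's routine view of the differential is reduced, which has to be squared with the duty to detect infections of special interest. Locally ordered tests remain visible, so protection is partial.

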11.2.7. Pregnancy Screen

Pregnancy screening for females of childbearing potential must be negative prior to IP administration. Pregnancy tests will be analyzed at a local laboratory.

A serum pregnancy test must be taken at Screening (Visits 1a and/or 1b) in women of childbearing potential (WOCBP) as described in the SoA (Table 5). A urine pregnancy test (human chorionic gonadotropin; dipstick) must be performed at the trial site at baseline prior to randomization in WOCBP, unless the Baseline Visit (Day 0) and Visit 1b are on the same day. The test must be repeated every 4 weeks as shown in the SoA (Table 5).

Additional serum or urine pregnancy tests may be performed, as determined necessary by the Investigator or required by local regulation, to establish the absence of pregnancy at any time during the participant's participation in the trial.

Pregnancy reporting requirements are found in Section 11.7.5 .

11.3. Safety Reporting Definitions

Investigators are responsible for the detection and documentation of events that meet the definition of an AE, SAE, AESI, suspected DILI, or UADE, as provided in this protocol.

Investigators must review the IB so as to be aware of the safety-related events, which may be anticipated with its use. Investigators should also be versed in the latest SoC guidelines.

